8.2. Safety assessments

The investigator and his/her designees are responsible for detecting, documenting, and reporting events that meet the definition of an AE, AESI or SAE. The investigator and designees are responsible for following up AEs that are serious, considered related to the study intervention or the study, or that caused the participant's withdrawal from the study intervention or study.

8.2.1. Pre-vaccination procedures

8.2.1.1. Collection of demographic data

Prior to study enrolment, demographic data will be collected from the participant, including date of birth (Phase I and Phase II (Sourcing): year; Phase II (Formulation and Schedule-finding): month and year), gender, race, ethnicity, weight, and height, and recorded in the participant's eCRF.

For Phase II (Formulation and Schedule-finding) only: At Visit V1 in the Control group, the participant receives 2 injections, one in either arm. Therefore, in order to associate the solicited events reported to the vaccine administered in that arm, the dominant arm (left or right) will be recorded in the eCRF ([Table 16](#)).

8.2.1.2. Medical/vaccination history

Obtain the participant's medical/vaccination history by interviewing the participant/parent(s)/LAR(s) and/or review of the participant's medical records. Record any pre-existing conditions, signs and/or symptoms present prior to the first dose of study intervention in the eCRF.

8.2.1.3. General and symptom-directed physical examination

A general physical examination is to be performed by a qualified healthcare practitioner. "Qualified health care practitioner" refers to any licensed or certified healthcare professional who is permitted by institutional policy to perform protocol-required procedures, and who is identified within the Delegation of Responsibility Log. The physical examination will include examination of organ systems that are relevant to the investigator based on medical history and review of systems and a measurement of heart rate, blood pressure, and temperature.

These data will be written in the source document. Should the physical assessment reveal any abnormal values or events, these must be documented in the eCRF Adverse Events Form.

Physical examination at each study visit subsequent to the first study intervention visit, will be performed only if the participant / participant's parent(s)/LAR(s) indicates during questioning that there might be some underlying pathology(ies) or if deemed necessary by the Investigator or delegate.

If the investigator determines that the participant's health on the day of vaccination temporarily precludes vaccination, the visit will be rescheduled. Treatment of any abnormality observed during this examination should be performed according to local medical practice outside this study or by referral to an appropriate health care provider.

8.2.1.4. Pregnancy test

Female participants of childbearing potential must perform a urine pregnancy test before the administration of any dose of study intervention. Pregnancy testing must be done even if the participant is menstruating at the time of the study visit. The study intervention may only be administered if the pregnancy test is negative.

Refer to the Section 10.5.3.1 for the information on study continuation for participants who become pregnant during the study.

8.2.1.5. Warnings and precautions to vaccination

Warnings and precautions to administration of study intervention must be checked at each visit with planned administration of study intervention.

Refer to the approved product label/package insert of *Bexsero* and *Menveo*.

8.2.2. Study holding rules and safety monitoring

[figure not shown]
Safety monitoring is specified in the endpoints (Section 9.4) as well as in Table 1 (for Phase I), Table 3 (for Phase II, Formulation and Schedule-finding) and Table 5 (for Phase II, Sourcing).

8.2.2.1. Safety data review

8.2.2.1.1. Safety evaluation

For Phase I of the study, a staggered enrolment of healthy volunteers will be performed, as described in Figure 4.

Figure 4 Step-wise approach for safety review in Phase I (Safety Lead-in)

Abbreviation: N, number of participants; V, clinic visit; D, day; iSRC, internal safety review committee; PC, phone contact; BS, blood sample.

Note: This is a simplified study design aimed to show the safety review in Phase I. To see the detailed study design, refer to Figure 1

[figure not shown]
An iSRC, composed of senior GSK experts independent from the study team, will meet at pre-defined timepoints to perform safety monitoring through unblinded review of safety data.

The following step-wise approach will be followed for the safety evaluation during the Phase I Safety Lead-in:

- Step 1: Following the first vaccination in [REDACTED] (12 participants) and [REDACTED] (4 participants) groups, all available safety data from all participants collected up to Day 8 will be evaluated by the iSRC. The iSRC will be responsible for making the first “go-no go” decision based on unblinded data. If a “go” decision is made, the enrolment in groups [REDACTED] will start and the administration of the second vaccination will take place in groups [REDACTED].
- Step 2: Following the first vaccination in [REDACTED] (12 participants) and [REDACTED] (4 participants) groups, all available safety data from all participants collected up to Day 8 will be evaluated by the iSRC. The iSRC will be responsible for making the second “go-no go” decision based on unblinded data. If a “go” decision is made, the administration of the second vaccination will take place for participants in groups [REDACTED].
- Step 3: Following the second vaccination in [REDACTED] groups at Day 31, all available safety data from all participants collected up to Day 38 will be evaluated by the iSRC. The iSRC will be responsible for making the third “go-no go” decision based on unblinded data. If a “go” decision is made, the Phase II enrolment will start parallelly for the 2 parts: Phase II (sourcing) and Phase II (formulation and schedule-finding).

For Phase II, Formulation and Schedule-finding part of the study, a staggered enrolment of healthy volunteers will be performed, as described in [Figure 5](#), for the iSRC safety evaluation of the first 45 enrolled participants (Phase II safety lead-in).

Figure 5 Step-wise approach for safety review in Phase II (Formulation and Schedule-finding)

Abbreviation: N, number of participants; V, clinic visit; D, day; TC, Telephone contact for Control group only; iSRC, internal safety review committee; PC, phone contact; BS, blood sample.

^ The phone call at Day 8 is only for the first 45 participants (15 participants in [REDACTED] 5 participants in [REDACTED] [REDACTED], 15 participants in [REDACTED] 5 participants in [REDACTED] and 5 participants in the Control groups)

Day 121 Month 4 is a visit for [REDACTED] groups (Visit V3) and is a telephone call for Control group (TC)

Note: This is a simplified study design aimed to show the safety review in Phase II (Formulation and Schedule-finding). To see the detailed study design, refer to [Figure 2](#) (*)

The following step-wise approach will be followed for the safety evaluation during the Phase II (Formulation and Schedule-finding):

- A total of 45 participants will be randomised with 3:1:3:1:1 ratio to the 5 groups (15 in the [REDACTED], 5 in the [REDACTED], 15 in the [REDACTED], 5 in the [REDACTED] and 5 in the Control group). A “go-no go” decision will be taken by the iSRC based on safety and reactogenicity data collected up to Day 8 from these participants (Section [8.2.2.1](#)).
- If the decision is “go”, the enrolment in all groups will continue with a randomisation ratio of 1:1:1:1:1 to the target total sample of 1000 participants and the administration of the second vaccination at Month 4 will take place in the 40 participants in [REDACTED] groups (as per study design).

Unblinded safety data to be reviewed by the iSRC include clinical safety laboratory data (only for Phase I), solicited administration site and systemic post-vaccination events, unsolicited AEs, AESIs, and SAEs. Additional safety data may be reviewed and monitored by the iSRC whenever applicable.

Continuous monitoring during the study by the study team will allow for ad-hoc iSRC reviews and/or enrolment hold if any safety concern is identified or a substantial trend emerges outside of the scheduled unblinded safety reviews. Holding rules will be introduced to ensure a well-controlled exposure to the investigational candidate vaccine and to prevent participants from being exposed to any unnecessary safety risks (refer to Section [8.2.2.1.3](#)).

8.2.2.1.2. *Outcome of safety evaluation*

If no safety signal is observed during the iSRC reviews, the favourable outcome of the safety evaluations will be documented and provided in a written way, authorising the investigator to start the administration of the subsequent dose of study intervention to participants, as well as enrolment and study intervention administration to the remaining participants in the next step of the study.

If a safety signal is observed during the safety evaluations or if any of the holding rules 2a-c is met ([Table 32](#)), the iSRC Chair (or his/her representative) is responsible for the urgent communication within GSK, including the rationale for the decision to put the study intervention administration on hold or not. Details about the procedures to be followed in case of safety signal or if a holding rule 2 (a-c) is met will be documented in the iSRC Charter.

The Clinical Research & Development Lead (CRDL) who is the primary study contact will inform the local GSK contact. All site staff will be informed about the final decision whether to suspend, modify or continue the conduct of the study on all groups or on selected groups by their local GSK contact.

8.2.2.1.3. *Study holding rules*

Holding rules are defined to ensure well-controlled exposure to the investigational product and they will apply to study participants in the Phase I Safety Lead-in and to the first 45 study participants enrolled in the formulation and schedule-finding Phase II part. The holding rules will hence serve as criteria to point attention to safety signals and require escalation within GSK, in order to decide whether other participants can be exposed. However, medical judgement considering all available safety data at the time of safety review should be the basis for decision to continue the study or not at each step.

The safety holding rules are defined in the [Table 32](#) (Phase I) and [Table 33](#) (Phase II, Formulation and Schedule-finding). If the investigator becomes aware of holding rule 1a-d being met (for Phase I) and holding rule 1a (for Phase II, Formulation and Schedule-finding during the safety lead-in step), he/she will suspend administering the study intervention and will inform GSK immediately (e.g. in case of death or any life-threatening SAEs).

Holding rules 2a-c will be assessed by the iSRC during the safety evaluations on unblinded data.

These holding rules have been written under the assumption that the safety data from all participants will be available. If the data from all participants are not available (i.e. in case a participant is lost to follow-up), then the holding rules will be assessed on a pro-rata basis.

Of note, no formal holding rules will be applied for other safety data such as missed visits due to study intervention related AEs, Grade 1 and Grade 2 solicited and unsolicited AEs in the 7-day follow-up period and unsolicited AEs collected from Day 8 to Day 30 after study intervention administration. However, if available, these data will also be reviewed by the iSRC to allow an overall assessment of the benefit/risk ratio of study intervention administration.

The iSRC can also meet ad-hoc during the entire safety lead-in phase (Phase I).

Table 32 Study holding rules – Phase I

Holding rule	Event	Number or % of participants needed to trigger the hold
1a	Death or any life-threatening SAE regardless of causality	≥ 1
1b	Any non-life-threatening SAE that can be reasonably attributed to the vaccination	≥ 1
1c	Any withdrawal from the study (by investigator or participant request) following a Grade 3 AE that can be reasonably attributed to the vaccination.	≥ 1
1d	Fever >40°C (104°F) OR any solicited administration site and/or systemic events leading to hospitalisation , OR necrosis at the injection site, each with an event onset within the 7-day (Day 1-7) post-vaccination period	≥ 1
2a	Any Grade 3 solicited administration site event (lasting 48h or more) in the investigational group, with an event onset within the 7-day (Day 1-7) post-vaccination period	≥ 20%
2b	Any Grade 3 solicited systemic event (lasting 48h or more) in an investigational group, with an event onset within the 7-day (Day 1-7) post-injection period	≥ 20%
2c	Any Grade 3 unsolicited AE in an investigational group, that can be reasonably attributed to the vaccination, with an event onset within the 7-day (Day 1-7) post-injection period OR Any Grade 3 abnormality in pre-specified haematological or biochemical laboratory parameters* in an investigational group with an event onset within the 7-day (Day 1-7) post-vaccination period	≥ 20%

Abbreviations: AE, adverse event; SAE, serious adverse event.

* Please refer to FDA Toxicology Grading Scale for the definition of the Toxicity Grading Scale for Healthy Adult and Adolescent Volunteers Enrolled in Preventive Vaccine Clinical Trials [[FDA](#), 2007; Refer to Section [10.4](#), Appendix 4]

Table 33 Study holding rules – Phase II (Formulation and Schedule-finding)

Holding rule	Event	Number or % of participants needed to trigger the hold
1a	Death or any life-threatening SAE regardless of causality	≥ 1
2a	Any Grade 3 solicited administration site event (lasting 48h or more) in the investigational group, with an event onset within the 7-day (Day 1-7) post-vaccination period	≥ 20%
2b	Any Grade 3 solicited systemic event (lasting 48h or more) in an investigational group, with an event onset within the 7-day (Day 1-7) post-injection period	≥ 20%
2c	Any Grade 3 unsolicited AE in an investigational group, that can be reasonably attributed to the vaccination, with an event onset within the 7-day (Day 1-7) post-injection period	≥ 20%

Abbreviations: AE, adverse event; SAE, serious adverse event;

The investigator is not permitted to begin dosing study participants in subsequent steps (Phase I or Phase II Formulation and Schedule-finding) until the receipt of favourable written documentation of iSRC safety evaluations.

If the investigator becomes aware of a holding rule being met, he/she must suspend administration of the study intervention and inform GSK immediately (holding rules 1a-d). Refer to [Table 40](#) for contact information.

The following communication sequence must be followed:

- The concerned site staff must put enrolment and study intervention administration on hold.
- The concerned site staff must immediately inform their local contact defined in the [Table 40](#).
- The LML will inform the other sites of his/her country, LMLs of other countries and the CRDL.
- All informed site staff will send back an email to their local contact to acknowledge receipt of the information.
- GSK Central will further evaluate the case with the iSRC and will take the decision to stop or to restart the vaccination. CRDL who is the primary contact will inform the local GSK contact. All site staff will be informed about that final decision by their local GSK contact.

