The intensity should be assigned to 1 of the following categories:

- 1 (mild) = An AE which is easily tolerated by the participant, causing minimal discomfort and not interfering with everyday activities.
- 2 (moderate) = An AE which is sufficiently discomforting to interfere with normal everyday activities.
- 3 (severe) = An AE which prevents normal, everyday activities (in a young child, such an AE would, for example, prevent attendance at school /a day-care centre and would cause the parent(s)/LAR(s) to seek medical advice. In adults/adolescents,

such an AE would, for example, prevent attendance at work/school and would necessitate the administration of corrective therapy.)

An AE that is assessed as Grade 3 (severe) should not be confused with an SAE. Grade 3 is a category used for rating the intensity of an event; and both AEs and SAEs can be assessed as Grade 3. An event is defined as 'serious' when it meets 1 of the pre-defined outcomes as described in the Section [10.3.2](#).

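### The Phase II lead-in (45 participants aged 10 to 25) drops, without a stated reason, the Phase I rule that one related non-life-threatening SAE pauses dosing

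*Protocol*

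**What the plan says.** Table 32 (Phase I) has four rules triggered by a single participant. Rule 1a is death or a life-threatening SAE. Rule 1b is "Any non-life-threatening SAE that can be reasonably attributed to the vaccination". Rule 1c is withdrawal after a related Grade 3 AE. Rule 1d is fever above 40°C, hospitalisation for a solicited event, or "necrosis at the injection site, each with an event onset within the 7-day (Day 1-7) post-vaccination period". Three further rules (2a-2c) are triggered at 20% of an investigational group.

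Table 33 (Phase II Formulation and Schedule-finding) keeps 1a and 2a-2c only. The text of section 8.2.2.1.3 matches: the investigator suspends dosing for 1a-d in Phase I, but only for "holding rule 1a (for Phase II, Formulation and Schedule-finding during the safety lead-in step". The paragraph after both tables says that on learning a holding rule is met "he/she must suspend administration of the study intervention and inform GSK immediately (holding rules 1a-d", without separating the phases.

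Section 8.2.2.1.3 states that the internal Safety Review Committee (iSRC) assesses rules 2a-c at its safety evaluations. Section 8.2.2.1.1 schedules one such evaluation in this part, on data to Day 8 from the 45. It also allows ad-hoc iSRC review or an enrolment hold if a safety concern is identified.

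**The concern.** Section 8.2.2.1.3 says the holding rules are there to keep exposure well controlled, and names these 45 participants as one of the two populations they cover. Phase I and the Sourcing part enrol adults only (section 5.1); the lead-in is open from age 10, although no minimum number of minors is stated. For one related non-life-threatening SAE the sponsor required a pause in adults. For the same event in the lead-in, dosing of the remaining participants can continue without breaching any protocol rule, and the protocol does not say why.

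What is at stake is the order of events: whether the iSRC looks at a related SAE before the next lead-in participant is injected, or possibly after.

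**Working it through.** No published figure has to be reproduced beyond the sizes, which agree: 15 + 5 + 15 + 5 + 5 = 45 and 45 + 955 = 1000.

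**1. The two tables side by side (section 8.2.2.1.3)**

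| Rule | Phase I | Phase II lead-in |
|---|---|---|
| 1a: death or life-threatening SAE | 1 participant | 1 participant |
| 1b: related non-life-threatening SAE | 1 participant | none |
| 1c: withdrawal after related Grade 3 AE | 1 participant | none |
| 1d: fever >40°C, hospitalisation, necrosis | 1 participant | none |
| 2a-2c: Grade 3 events | 20% of a group | 20% of a group |

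Table 32 carried 1b alongside 2c, so in Phase I the 20% rules were not treated as a substitute for it.

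**2. Can rules 2a-c stand in for 1b?**

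- Count: 0.20 × 15 = 3 and 0.20 × 5 = 1. In a 15-person group one event is 1/15 = 6.7% and two are 2/15 = 13.3%, both below the trigger. In a 5-person group one qualifying event is 1/5 = 20% and meets it.
- Grade: rule 2c counts "Any Grade 3 unsolicited AE in an investigational group, that can be reasonably attributed to the vaccination". Section 10.3.9.1 separates grade from seriousness: "An AE that is assessed as Grade 3 (severe) should not be confused with an SAE". A related SAE graded 1 or 2 does not count.
- Onset: rules 2a-c count Days 1-7 only. The section states that no formal rule applies to "unsolicited AEs collected from Day 8 to Day 30 after study intervention administration".
- Timing: they are assessed at an iSRC evaluation, not when the event occurs. Under section 8.2.2.1.2 the outcome is a decision to hold or not to hold.

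**3. Where lead-in doses fall relative to the one scheduled review**

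Group labels are redacted. From the group order in section 4.1.2.1, the 15-person groups appear to be the 0,6-month schedule and the 5-person groups the 0,2-month schedule. Table 11 treats Day 31 as three months before first vaccination in one set of groups, so the 0,2-month groups have their first active dose at Month 4. On that reading:

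| Time | Investigational doses in the lead-in |
|---|---|
| Day 1 | 15 + 15 = 30 |
| Month 4 | 5 + 5 = 10 (first active dose) |
| Month 6 | 30 + 10 = 40 |
| Total | 80, of which 10 + 40 = 50 (62.5%) follow the Day 8 review |

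Those 50 doses are not unreviewed: the Month 4 injections wait for the iSRC's decision, which takes SAEs into account. The count shows only how many doses come after the last scheduled look.

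**4. Following one related, non-life-threatening SAE through the lead-in**

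- Onset while others still await their Day 1 dose: reported within 24 hours, but no required pause for the others.
- Onset in the Day 8 data: reviewed before the Month 4 injections and before the 955 are dosed. Covered.
- Onset after the Day 8 data, before Month 4: ad-hoc review is possible but not required.
- Onset after a Month 4 or Month 6 injection: the same, and no further review is scheduled.

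In every case section 7.1.1 stops further doses for the affected participant only.

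**5. What rule 1b alone would restore**

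Hospitalisation makes an event an SAE (section 10.3.2), and all solicited events are taken as related (section 10.3.9.2). Hospitalisation for a solicited event, part of 1d, therefore falls under 1b. Necrosis would be caught when it meets an SAE criterion. Rule 1c and fever above 40°C without hospitalisation would not.

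**The case against.** The strongest reply is that the easing is deliberate. The text names 1a-d for one phase and 1a for the other. Phase II opens only after three unblinded iSRC decisions, the last after second doses of the higher-dosage formulation, and the vaccine builds on two licensed products. Fewer automatic triggers after a first-in-human step is a defensible policy. This stands for 1c and for the fever part of 1d, where one short fever would stop dosing. It is weaker for 1b. Phase I vaccinates 24 adults and no minors, and even zero events in 24 leaves a one-sided 95% upper bound of 1 − 0.05^(1/24) = 11.7% per participant.

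Second, the remaining controls are substantial. SAEs reach the sponsor within 24 hours (sections 8.3.1 and 8.3.3), and the study team monitors continuously. The sentence "The iSRC can also meet ad-hoc during the entire safety lead-in phase (Phase I") names Phase I, but the ad-hoc provision in section 8.2.2.1.1 is not so limited, so little rests on it. Detection and escalation are in place; the automatic pause is what is missing.

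Third, the iSRC Charter holds the procedures for a safety signal and is not among the documents. It may add a pause.

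Fourth, the change may come too late. By Protocol Amendment 4 (22 March 2022), 107 Sourcing participants were enrolled, and both Phase II parts were to open in parallel. The SAP is dated August 2023. Lead-in dosing was probably over, though neither document says so.

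**Conclusion.** The gap is real and narrow. In the protocol text, a related non-life-threatening SAE in the Phase II lead-in triggers no mandatory pause for the other lead-in participants, during Day 1 dosing or after the Day 8 review. Phase I required one, and no reason is given for the change. Severity is low to moderate; this is a cheap improvement.

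Three stronger readings are tempting and unsupported. A reader might infer that the 955 later participants are exposed, but section 8.2.2.1.3 forbids dosing in the next step until a favourable written iSRC outcome. A reader might infer that such SAEs go unreviewed, but those in the Day 8 data are seen before Month 4. A reader might infer that a known share of doses would be prevented, but that needs an event risk and an enrolment pace, and the documents give neither; a hold also pauses doses and need not cancel them.

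Nor does the general sentence citing 1a-d show that 1b applies in Phase II, because Table 33 defines no such rule.

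The conclusion rests on the protocol text without the Charter. Only the remark about first active doses at Month 4 depends on the inferred group labels.

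**What to change.** Add rule 1b to Table 33 at one participant, for the 45 lead-in participants, as an investigator-triggered hold lifted by an ad-hoc iSRC review. In section 8.2.2.1.3, change the Phase II suspension duty from 1a to 1a-b, and make the sentence after Table 33 state the rules by phase (1a-d for Phase I, 1a-b for Phase II). Give a one-sentence reason for not carrying over 1c and the rest of 1d; restoring them is optional.

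The cost is one table row and a few words, with no added data or participants, and an occasional short pause. If lead-in dosing has begun, the rule covers the remaining lead-in doses only. If it is complete, only the alignment of the wording is left to do.
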